7.2 PARTICIPANT DISCONTINUATION/WITHDRAWAL FROM STUDY

Participants are free to withdraw from participation in the study at any time upon request.

In addition, the investigator has the right to withdraw a patient from the study at any time should any untoward effect occur. In addition, a participant may be discontinued from study treatment by the investigator or the Sponsor if study treatment is inappropriate, the trial plan is violated, or for administrative and/or other safety reasons. Specific details regarding procedures to be performed at study treatment discontinuation are provided in Section 8.1.4.1.

A participant must be discontinued from study treatment but continue to be monitored in the study and moved to survival follow-up for any of the following reasons:

- The participant or participant's legally acceptable representative requests to discontinue study treatment
- Confirmed radiographic disease progression outlined in Section 8.1.2.6
- Any progression or recurrence of any malignancy, or any occurrence of another malignancy that requires active treatment

Note: Participants with basal cell carcinoma of the skin, squamous cell carcinoma of the skin, or carcinoma in situ (excluding carcinoma in situ of the bladder) who have undergone potentially curative resection do not have to discontinue study intervention.

- Unacceptable adverse experiences as described in Appendix 5 and Appendix 6.
- The participant has a medical condition or personal circumstance which, in the opinion of the treating investigator and/or sponsor, placed the participant at unnecessary risk from continued administration of study treatment.
- Sponsor-Investigator determines it is in the best interest of the patient
- Patient non-compliance with the study treatment or procedure as determined by the treating investigator
- The participant has a confirmed positive serum pregnancy test
- Recurrent Grade 2 pneumonitis
- Discontinuation of treatment may be considered for participants who have attained a confirmed complete response (CR) and have been treated for at least 8 cycles (at least 24 weeks), receiving 2 cycles of the combination including 2 doses of pembrolizumab and at least 80% of the planned doses of olaparib and pembrolizumab beyond the date when the initial CR was declared. These participants may be eligible for second course treatment described in Appendix 7.
- Administrative reasons

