8.1.2.6.2 END OF TREATMENT AND FOLLOW-UP TUMOR IMAGING

In participants who discontinue study treatment, tumor imaging should be performed at the time of treatment discontinuation (\pm 7 days). If previous imaging was obtained within

8 weeks prior to the date of discontinuation, then imaging at treatment discontinuation is not mandatory. In participants who discontinue study treatment due to documented disease progression and the Investigator elects not to implement iRECIST, this is the final required tumor imaging.

In participants who discontinue study treatment without documented disease progression, every effort should be made to continue monitoring their disease status by tumor imaging every 12 weeks to monitor disease status until the start of a new anticancer treatment, disease progression, pregnancy, death, withdrawal of consent, or the end of the study, whichever occurs first.

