8.1.4 OTHER PROCEDURES

8.1.4.1 WITHDRAWAL/DISCONTINUATION

When a participant discontinues/withdraws prior to trial completion, all applicable activities scheduled for the final trial visit should be performed at the time of discontinuation. Any adverse events which are present at the time of discontinuation/withdrawal should be followed in accordance with the safety requirements outlined in Section 8.4. Participants who a) attain a CR or b) complete 24 months of treatment with pembrolizumab may discontinue treatment with the option of restarting treatment if they meet the criteria specified in Appendix 7. After discontinuing treatment following assessment of CR, these participants should return to the site for a Safety Follow-up Visit (described in Section 8.3) and then proceed to the Follow-Up Period of the study (described in Section 8.3).

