8.1.4.3 POST-TREATMENT VISITS

Safety Follow-Up Visit

The mandatory Safety Follow-Up Visit should be conducted approximately 30 days after the last dose of study treatment or before the initiation of a new anti-cancer treatment, whichever comes first. If the post-trial visit occurs less than 30 days after the last dose of study treatment, a subsequent follow-up phone call should be made at 30 days post the last dose of study treatment to determine if any adverse events have occurred since the post-trial clinic visit. All AEs that occur prior to the Safety Follow-Up Visit should be recorded. Participants with an AE of Grade > 1 will be followed until the resolution of the AE to Grade 0-1 or until the beginning of a new anti-cancer therapy, whichever occurs first. SAEs that occur within 90 days of the end of treatment or before initiation of a new anti-cancer treatment will also be followed and recorded. Participants who are eligible for retreatment/crossover with pembrolizumab (as described in Appendix 7) may have up to two safety follow-up visits, one after the Initial Treatment Period and one after the Second Course Treatment.

Follow-Up Visits

Participants who discontinue study treatment for a reason other than disease progression will move into the Follow-Up Phase and should be assessed every 12 weeks (42 ± 7 days) by radiologic imaging to monitor disease status. Every effort should be made to collect information regarding disease status until the start of new anti-cancer therapy, disease progression, death, end of the study or if the participant begins retreatment with pembrolizumab as detailed in Appendix 7. Information regarding post-study anti-cancer treatment will be collected if new treatment is initiated.

Participants who are eligible to receive retreatment with pembrolizumab according to the criteria in Appendix 7 will move from the follow-up phase to the Second Course Phase when they experience disease progression.

Survival Follow up

Participants who experience confirmed disease progression or start a new anticancer therapy, will move into the Survival Follow-Up Phase and should be contacted by telephone every 12 weeks to assess for survival status until death, withdrawal of consent, or the end of the trial, whichever occurs first. Patients will be followed for 5 years for survival.

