APPENDIX 7: SECOND COURSE FOR PEMBROLIZUMAB

All participants who stop study treatment with SD or better may be eligible for up to an additional 17 cycles (approximately 1 year) of pembrolizumab treatment if they progress after stopping study treatment from the initial treatment phase. This retreatment is termed the Second Course Phase of this study and is only available if the study remains open and the participant meets the following conditions:

Either

- Stopped initial treatment with study treatment after attaining an investigator-determined confirmed CR based on RECIST 1.1, and
 - Was treated with at least 8 cycles of study treatment before discontinuing treatment, and
 - Received at least 2 treatments with pembrolizumab beyond the date when the initial CR was declared

OR

- Had SD, PR, or CR and stopped study treatment after completion of 35 administrations (approximately 2 years) of study treatment for reasons other than disease progression or intolerability

AND

- Experienced an investigator-determined radiographic disease progression by RECIST 1.1 after stopping initial treatment, and
 - Upon unblinding at the time of centrally verified disease progression were found to have received pembrolizumab, and
 - No new anticancer treatment was administered after the last dose of study treatment, and
 - The participant meets all of the safety parameters listed in the inclusion criteria and none of the safety parameters listed in the exclusion criteria, and
 - The study is ongoing

An objective response or disease progression that occurs during the Second Course Phase for a participant will not be counted as an event for the primary analysis of either endpoint in this study.

**Note: patients must have measurable disease at the start of protocol treatment to be eligible for this provision.*

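### Section 7.2 sends patients who stop treatment without progression to telephone survival follow-up, against the 12-weekly imaging planned elsewhere; as written it would lose progression dates for PFS and DoR

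*Combined protocol and SAP*

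**What the plan says.** Section 7.2 introduces its list of mandatory stops by saying that the participant is to "continue to be monitored in the study and moved to survival follow-up for any of the following reasons". Besides confirmed radiographic progression, the list holds participant request, unacceptable adverse experiences, recurrent Grade 2 pneumonitis, non-compliance, administrative reasons, and an optional stop after confirmed CR. Of the CR patients it adds: "These participants may be eligible for second course treatment described in Appendix 7".

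Section 8.1.4.3 defines two separate phases. On the first: "Participants who discontinue study treatment for a reason other than disease progression will move into the Follow-Up Phase", where disease status is followed by imaging every 12 weeks. On the second, those with "confirmed disease progression or start a new anticancer therapy, will move into the Survival Follow-Up Phase and should be contacted by telephone", at 12-week intervals, to record survival status. It also says that participants eligible for retreatment "will move from the follow-up phase to the Second Course Phase when they experience disease progression".

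Section 8.1.2.6.2 has patients who stop without documented progression monitored "by tumor imaging every 12 weeks to monitor disease status until the start of a new anticancer treatment", or until another listed end point such as progression, pregnancy or death. Footnotes n and r of the Schedule of Events (1.3) say much the same, and its 12-weekly Follow Up column marks both survival status and tumor imaging. For patients who stop after CR, 8.1.4.1 prescribes a safety visit "and then proceed to the Follow-Up Period of the study". Appendix 7 makes this a condition for a second course: "Experienced an investigator-determined radiographic disease progression by RECIST 1.1 after stopping initial treatment".

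Section 9.1 runs PFS to progression or to last follow-up, and DoR from response to progression. Section 9.4.3 analyses both by Kaplan-Meier, without a formal test and without a censoring rule.

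**The concern.** A patient who stops for toxicity, at their own request or after CR receives two incompatible instructions: telephone contact for survival under 7.2, and scans every 12 weeks under the other sections. A site that follows 7.2 stops looking for progression in patients whose disease is still controlled. Their progression dates are then missing from PFS and, for responders, from DoR.

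DoR is the more exposed endpoint because 9.3 limits it to responders. At the null and alternative ORR of 9.2 that is 26 × 0.25 = 6.5 to 26 × 0.45 = 11.7 patients, so each lost date weighs heavily. Patients who might be offered a second course would also lose the surveillance scans on which their progression would normally be seen.

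**Working it through.** The plan gives no figure on this point to reproduce. The main check compares the rules; the arithmetic after it is illustration only.

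**1. Where each kind of stop is sent**

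| Reason listed in 7.2 | Under 7.2 | Under the other sections |
|---|---|---|
| Confirmed radiographic progression | Survival follow-up | Survival Follow-Up (8.1.4.3): agrees |
| Request, unacceptable AE, recurrent Grade 2 pneumonitis, non-compliance, administrative | Survival follow-up | Follow-Up Phase, imaging every 12 weeks (8.1.4.3, 8.1.2.6.2, footnotes n and r): conflicts |
| Optional stop after CR | Survival follow-up | Follow-Up Period (8.1.4.1), the phase from which the second course is entered (8.1.4.3): conflicts |
| Pregnancy | Survival follow-up | Imaging ends at pregnancy (8.1.2.6.2): no loss of scans |
| Another malignancy needing active treatment | Survival follow-up | Imaging ends once new anticancer therapy starts: no loss from then |

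The statement in 7.2 that patients stay monitored does not settle the conflict, because the same sentence names the phase and 8.1.4.3 defines that phase as telephone contact.

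**2. Progression dates at risk**

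The documents give neither the share who stop without progression nor an expected PFS. Assumed: 10/20/30% stop without progression; exponential time to progression, median 4 months; stopping independent of progression; median survival after progression 6 months; scans every 9 weeks on treatment; no new therapy; every planned scan done.

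- Patients who stop: 26 × 0.10/0.20/0.30 = 2.6/5.2/7.8.
- Progressions among them that 12-weekly scans would have dated (simulation, 3000 trials of 26): 2.2/4.4/6.5.
- If a fraction f starts new therapy at once, their imaging ends under 8.1.2.6.2 as well, so the loss is about (1 − f) times as large. For f = 0.5: 1.1/2.2/3.3. For f = 0.8: 0.4/0.9/1.3.

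**3. Effect of 7.2 alone on 12-month PFS**

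Same model, deaths counted as events on the imaging path. Under 7.2, patients are censored at the last scan. Entries are for 10/20/30% stopping.

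| Median time to progression | 12-weekly imaging, % | 7.2 followed, % | Difference, points |
|---|---|---|---|
| 3 months | 8.7/8.8/8.5 | 8.3/7.9/7.5 | 0.4/0.9/1.0 |
| 4 months | 16.2/16.0/15.8 | 15.7/15.1/14.2 | 0.5/0.9/1.6 |
| 6 months | 29.7/29.3/29.2 | 29.3/28.6/27.8 | 0.4/0.7/1.4 |

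For comparison, the standard error of a 16% proportion in 26 patients is √(0.16 × 0.84 / 26) = 0.072, about 7 points.

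**4. What the PFS definition adds**

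If PFS is also run to the last telephone contact, as 9.1 permits, 12-month PFS at the 4-month median becomes 19.2/22.1/25.3% against 16.2/16.0/15.8%, with deaths as events on both paths. Section 9.1 does not name death as a PFS event. With deaths censored on both paths the figures are 25.0/30.8/37.2% against 20.0/20.0/19.9%. These shifts need the 9.1 wording as well as 7.2, and they too assume no new therapy.

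**The case against.** The strongest reply is that the plan already gives the answer. The Schedule of Events, 8.1.2.6.2, 8.1.4.1 and 8.1.4.3 agree with one another, and 7.2 is the only outlier. Just above its list, 7.2 also refers procedures at discontinuation to 8.1.4.1, which routes CR patients correctly. Most sites would probably keep scanning. This stands as a reason to rate the point low. It does not remove the conflict: 8.1.4.1 names the Follow-Up Period only for CR, 7.2 is the section a site consults when a patient stops, and no rule says which section prevails.

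A reader might infer more than the documents support:

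- **That every patient who stops loses imaging.** Section 7.2 covers listed reasons only, and completing 24 months of pembrolizumab is not named among them. For progression, pregnancy or new anticancer therapy, the routes coincide or imaging ends anyway.
- **That no scan could support a second course.** Section 8.1.2.6.3 requires imaging within 14 days before pembrolizumab is restarted, read locally to determine eligibility. What 7.2 removes is the surveillance before that scan.
- **That 7.2 inflates 12-month PFS to 19–25% or more.** That shift also needs PFS to run to a contact date. Section 7.2 alone lowers the estimate slightly.
- **That the primary analysis is affected.** Any effect on ORR is limited to a responder who stops before the confirmation scan required by 8.1.2.6.1, and the documents give no rate for this.

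**Conclusion.** The conflict is real and stands in current text. For stops without progression, 7.2 is wrong as written: it names a phase that 8.1.4.3 keeps for other patients. If followed, it loses surveillance scans, and so PFS and DoR progression dates, in patients who have not started new therapy.

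How many is unknown. The 2/4/7 of 26 is an upper bound within the assumed 10/20/30% stopping rates, because the calculation has no new-therapy term and assumes full scan adherence. The movement in 12-month PFS from 7.2 alone, at most about 2 points, is small beside a sampling error of about 7. It rests on stopping being independent of progression. If patients who stop for toxicity or CR have a different progression risk, the censoring would be informative, and the documents offer nothing from which to size that.

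PFS and DoR are descriptive, so no formal test changes. The use of last follow-up in 9.1 is a separate weakness, and the larger PFS shifts depend on it. Overall this is a minor point, worth correcting because the correction costs almost nothing.

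**What to change.** In 7.2, limit the move to survival follow-up to confirmed progression (or documented progression after which 8.1.2.6.2 ends imaging) or the start of new anticancer therapy. Send every other listed reason, including the stop after CR, to the imaging Follow-Up Phase of 8.1.4.3. Apply the schedule and end rules of 8.1.2.6.2, which also cover pregnancy. Cite 8.1.2.6.2 for the interval because 8.1.4.3 glosses 12 weeks as 42 days, although 12 × 7 = 84.

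In 9.1 and 9.4.3, state that PFS and DoR without progression are censored at the last tumor assessment, not at the last contact.

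The cost is wording in three sections. It adds no scans beyond those already planned in the Schedule of Events, 8.1.2.6.2 and 8.1.4.3, and leaves the sample size and the primary test unchanged.

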7.3 LOST TO FOLLOW-UP

A subject will be considered lost to follow-up if he or she fails to return for three scheduled visits and is unable to be contacted by the study staff. The following actions must be taken if a subject fails to return to the clinic for a required study visit:

- Site will attempt to contact the subject and reschedule the missed visit, as well as advise subject on importance of maintaining assigned visit schedule.
- Before a subject is deemed lost to follow-up, the delegated study staff will make every effort to regain contact with the subject with 3 required contact attempts. These contact attempts should be documented in the subject's medical record or study file.
- Should the subject continue to be unreachable, he or she will be considered lost to follow up and withdrawn from the study. No additional data/survival status will be collected from then on.

8 STUDY ASSESSMENTS AND PROCEDURES

8.1 STUDY PROCEDURES

The Schedule of Events - **Section 1.3** summarizes the trial procedures to be performed at each visit. Individual trial procedures are described in detail below. It may be necessary to perform these procedures at unscheduled time points if deemed clinically necessary by the investigator.

Furthermore, additional evaluations/testing may be deemed necessary by the Sponsor-Investigator and/or Merck for reasons related to participant safety. In some cases, such evaluation/testing may be potentially sensitive in nature (e.g., HIV, Hepatitis C, etc.), and thus local regulations may require that additional informed consent be obtained from the participant. In these cases, such evaluations/testing will be performed in accordance with those regulations.

8.1.1 ADMINISTRATIVE PROCEDURES

8.1.1.1 INFORMED CONSENT

The Investigator must obtain documented consent from each potential participant prior to participating in a clinical trial.

General Informed Consent

Consent must be documented by the participant's dated signature or by the participant's legally acceptable representative's dated signature on a consent form along with the dated signature of the person conducting the consent discussion.

A copy of the signed and dated consent form should be given to the participant before participation in the trial.

The initial informed consent form, any subsequent revised written informed consent form and any written information provided to the participant must receive the IRB/ERC's approval/favorable opinion in advance of use. The participant or his/her legally acceptable representative should be informed in a timely manner if new information becomes available that may be relevant to the participant's willingness to continue participation in the trial. The communication of this information will be provided and documented via a revised consent form or addendum to the original consent form that captures the participant's dated signature or by the participant's legally acceptable representative's dated signature.

Specifics about a trial and the trial population will be added to the consent form template at the protocol level.

The informed consent will adhere to IRB/ERC requirements, applicable laws and regulations and Sponsor requirements.

8.1.1.2 MEDICAL HISTORY

A medical history will be obtained by the investigator or qualified designee. Medical history will include all active conditions, and any condition diagnosed within the prior 10 years that are considered to be clinically significant by the Investigator. Details regarding the disease for which the participant has enrolled in this study will be recorded separately and not listed as medical history.

8.1.1.3 DISEASE DETAILS AND TREATMENTS

8.1.1.3.1 DISEASE DETAILS

The investigator or qualified designee will obtain prior and current details regarding disease status.

8.1.1.3.2 PRIOR TREATMENT DETAILS

The investigator or qualified designee will review all prior cancer treatments including systemic treatments, radiation and surgeries.

8.1.1.3.2 SUBSEQUENT ANTI-CANCER THERAPY STATUS

The investigator or qualified designee will review all new anti-neoplastic therapy initiated after the last dose of trial treatment. If a participant initiates a new anti-cancer therapy within 30 days after the last dose of trial treatment, the 30 day Safety Follow-up visit must occur before the first dose of the new therapy. Once new anti-cancer therapy has been initiated the participant will move into survival follow-up.

8.1.1.3.2 RESTING 12-LEAD ECG

ECGs are required within 7 days prior to starting study treatment and when clinically indicated.

Twelve-lead ECGs will be obtained after the patient has been rested in a supine position for at least 5 minutes in each case. The Investigator or designated physician will review the paper copies of each of the 12-lead ECGs on each of the study days when they are collected.

ECGs will be recorded at 25 mm/sec. All ECGs should be assessed by the investigator as to whether they are clinically significantly abnormal / not clinically significantly abnormal. If there is a clinically significant abnormal finding, the Investigator will record it as an AE on the eCRF. The original ECG traces must be stored in the patient medical record as source data.

8.1.2 CLINICAL PROCEDURES/ASSESSMENTS

8.1.2.1 ADVERSE EVENT (AE) MONITORING

The investigator or qualified designee will assess each participant to evaluate for potential new or worsening AEs as specified in the Schedule of Events and more frequently if clinically indicated.

Adverse experiences will be graded and recorded throughout the study and during the follow-up period according to NCI CTCAE Version 5.0 (see Appendix 2). Toxicities will be characterized in terms regarding seriousness, causality, toxicity grading, and action taken with regard to trial treatment.

Please refer to section 8.4 for detailed information regarding the assessment and recording of AEs.

8.1.2.2 FULL PHYSICAL EXAM

The investigator or qualified designee will perform a complete physical exam during the screening period. Clinically significant abnormal findings should be recorded as medical history.

